11.2. Grading of Adverse Events using Common Terminology Criteria (CTCAE)

Adverse events (toxicities) will be graded according to the National Cancer Institute CTCAE version 5.0 for reporting of adverse events. A copy of the current version of the CTCAE version 5.0 can be downloaded from the CTEP home page:

https://ctep.cancer.gov/protocolDevelopment/electronic_applications/ctc.htm

11.3. Attribution

Definitions of relationship to study medication are as follows:

- **UNRELATED:** bears no relation to timing of medication, similar to symptoms or signs expected in the disease process, does not recur on rechallenge.
- **UNLIKELY:** does not have temporal relationship to intervention, could readily have been produced by the participant's clinical state, environmental, or other interventions, does not reappear or worsen with reintroduction of intervention.
- **POSSIBLY:** bears relation to timing of medication, similar to symptoms or signs expected in the disease process, does not recur on rechallenge.
- **PROBABLY:** bears clear relation to timing of medication, distinct from symptoms or signs expected in the disease process, does not recur on rechallenge.
- **DEFINITELY:** bears clear relation to timing of medication, distinct from symptoms or signs expected in the disease process, occurs on rechallenge.

Adverse events can be "Expected" or "Unexpected".

Expected adverse event

Expected adverse events are those that have been previously identified as resulting from administration of the agent. For the purposes of this study, expected adverse events are those adverse events that are listed or characterized in the Package Insert or current Investigator's Brochure (IB).

Unexpected adverse event

For the purposes of this study, unexpected adverse events are those not listed in the current Investigator Brochure or not identified. This includes adverse events for which the specificity or severity is not consistent with the description in the package insert or IB.

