ANC < 750/mm ³	
Interrupt study drug until resolution to ≥ 750/mm³. If the event resolves within 21 days, then study drug may be restarted at the same dose. If event resolves between days 22 and 28, restart at lower dose of 10 mcg/kg/dose.
 
If ANC is < 750/mm³ greater than 28 days after dose reduction, and at least “possibly” attributed to the study drug, the participant will be taken off protocol therapy.
 
Transient and repeated neutropenia is not unexpected and does not require permanent removal from study therapy unless deemed medically necessary by the treating physician after discussion with the principal investigator or study team.

---------------------------	---

All other adverse events (suspected to be related to the study drug)	
Grade 1-2	
Grade 1 AE continue drug same dose 20 mcg/kg/dose. Provide specific therapy to address symptoms.
 
If the event is an intolerable Grade 2 AE, not responsive to a specific therapy, consider study drug interruption until resolution to Grade ≤1. If the event is clinically significant and resolves within 21 days, then study drug may be restarted at same dose. If event resolves between days 22 and 28, restart at a lower dose of 10 mcg/kg/dose. If the patient continues to have grade 2 intolerable toxicity despite dose reduction and providing specific therapy to address symptoms, protocol therapy will be permanently discontinued.

Grade 3 and Grade 4	
Interrupt study drug until resolution to Grade ≤1. If the event resolves within 21 days, then study drug may be restarted at the same dose. If event resolves between days 22 and 28, or the patient has a repeat grade 3 or grade 4 event, restart at lower dose of 10 mcg/kg/dose. If toxicity returns

	to grade 3 or 4 after drug reduction, protocol therapy will be permanently discontinued.
--	--

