7. Tuberculosis (TB) in Mice: Mouse studies have reported a risk of worsening of TB in mice already infected with TB that are treated with Interferon or with poly-ICLC. Temporary worsening of TB has also rarely been reported in patients treated with high doses of interferon.

8. Transient anaphylactic reaction: There have been reports of transient anaphylactic reaction to the combination of a personalized glioma vaccine, GM-CSF, and poly-ICLC in glioblastoma patients. GM-CSF is known to cause anaphylaxis, but there have been no previous such reports in patients receiving poly-ICLC alone or with other vaccines.

9. Transient peritumoral edema: In a pilot brain tumor trial, a few patients showed an increase in gadolinium enhancing lesions after 3 - 6 months of IM poly-ICLC, followed by an apparent tumor response at 6 - 12 months and prolonged survival on continued treatment. Dexamethasone was used as needed in the first few months of treatment on that study. In a more recent follow-up open study in patients with advanced recurrent gliomas, several patients have shown increased peritumoral edema after several weeks of poly-ICLC therapy. This has resolved in all cases on continued poly-ICLC, with or without concomitant steroids. Biopsy data in at least two patients treated with poly-ICLC also showed a peritumoral inflammatory response. Likewise, in a dendritic cell vaccination trial in recurrent glioma patients with twice-weekly application of poly-ICLC IM, remarkable post-vaccination immune cell infiltration into the tumor was seen. These findings are commonly reported with other immunotherapies, and they raise the possibility that poly-ICLC may at times be facilitating a relatively early immunologic response to the tumor, perhaps manifested by transient increased edema or gadolinium enhancement. In line with this, one case of post-vaccination brain edema (Grade 3) possibly related to poly-ICLC adjuvant vaccination of a multi-peptide vaccine was reported from a Phase I trial in glioblastoma.

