11.4. Reporting Procedures for All Adverse Events

All observed or volunteered adverse events, regardless of suspected causal relationship to study drug, will be recorded as Adverse Events in the electronic case report forms and submitted via eDCS within 14 days of completion of each treatment cycle. Events involving adverse drug reactions, illnesses with onset during the study, or exacerbation of pre-existing illnesses should be recorded. Objective test findings (e.g. abnormal laboratory test results) should also be recorded if considered to be clinically significant by the treating investigator.

It will be left to the investigator's clinical judgment whether or not an adverse event is of sufficient severity to require that the participant should be removed from treatment. A participant may also voluntarily withdraw from treatment due to what he or she perceives as an intolerable adverse

event. If either of these occurs, the participant will be given appropriate care under medical supervision until symptoms cease or until the condition becomes stable.

The severity of toxicities will be graded in accordance with the Common Terminology Criteria for Adverse Event (CTCAE) version 5.0 ([CTCAE v5 Quick Reference](#)).

The relationship of adverse events to the study medications will be assessed by means of the question: "Is there a reasonable possibility that the event may have been caused by the study medication?", Please answer Yes or No.

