In addition, on this study, the research monitor is specifically required to review all unanticipated problems involving risk to participants or others, serious adverse events and all participant deaths associated with the protocol and provide an unbiased written report of the event. At a minimum, the research monitor should comment on the outcomes of the event or problem, and in the case of a serious adverse event or death, comment on the relationship to participation in the study. The research monitor should also indicate whether he/she concurs with the details of the report provided by the study investigator.

Safety Monitoring Criteria

Table 14 below defines the maximum allowed number of Grade 4 adverse events that are at least possibly attributable to the study drug.

If the number of events exceeds the number in the second column, accrual to the study should be placed on hold for safety evaluation, pending review of toxicities by the study committee in consultation with the DSMB and the research monitor, to determine whether the study should continue, be amended, or be terminated. For example, if 2 or more patients experience an event before the sixth patient begins therapy, the trial will be on hold.

Table 14. Safety Rules for Grade 4 Adverse Events

Number of Patients	Maximum Number Permitted	Probability to Stop	Cumulative Probability to Stop
5	1	0.081	0.081
10	2	0.070	0.151
16	3	0.068	0.219

Statistical Justification: The trial should hold enrollment and have a DSMB evaluation for safety if the probability that a Grade 4 adverse event (defined above) exceeds 10% is equal to or higher than 0.95, i.e., stop if $\Pr\{\Theta > 0.10 | \text{data}\} \geq 0.95$. The table above gives the safety rule for each set of 5 participants that enrolls in the study, with column 2 indicating the maximum number of cases of events that are permitted. The third column gives the probability of holding enrollment on the trial when in fact, the true $\Theta = 0.10$. Safety rules were generated using a binomial distribution.

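### Section 11.3 has no category for a disease-like event that recurs on rechallenge, and the relatedness variable behind the Table 14 hold is not fixed

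*Combined protocol and SAP*

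**What the plan says.** Section 11.3 (Attribution) gives five categories. Each joins three elements: timing, likeness to the disease, and what happens on rechallenge.

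- An event is placed in UNRELATED when it "bears no relation to timing of medication, similar to symptoms or signs expected in the disease process, does not recur on rechallenge".
- The next level, UNLIKELY, asks for no temporal link, an explanation in the participant's condition or other causes, and an event that "does not reappear or worsen with reintroduction of intervention".
- An event is placed in POSSIBLY when it "bears relation to timing of medication, similar to symptoms or signs expected in the disease process, does not recur on rechallenge".
- The next level, PROBABLY, asks for clear timing and an event unlike the disease, and keeps the same non-recurrence condition as POSSIBLY.
- The top level, DEFINITELY, matches PROBABLY on timing and distinctness, but here the event does come back when drug is given again.

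Three other sections depend on relatedness.

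- Section 12 uses Table 14 to set "the maximum allowed number of Grade 4 adverse events that are at least possibly attributable to the study drug". Its worked example counts patients: two or more before the sixth starts therapy puts the trial on hold.
- Section 6.4 limits its rules to toxicities that are at least possibly related. For Grade 3–4 events it says "If the event resolves within 21 days, then study drug may be restarted at the same dose", and it also provides for a repeat Grade 3 or 4 event.
- Section 11.4 assesses relationship with one question, "Is there a reasonable possibility that the event may have been caused by the study medication", answered Yes or No.

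Section 6.6 lists seizures and peritumoral edema among reported effects. On edema it says "several patients have shown increased peritumoral edema after several weeks of poly-ICLC therapy".

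**The concern.** Return of an event when drug is restarted normally strengthens the case that the drug caused it. In section 11.3 it does the opposite for an event that looks like the underlying tumor: recurrence disqualifies the event from POSSIBLY, and likeness to disease disqualifies it from DEFINITELY. The trial enrolls patients with brain and spinal cord gliomas, doses twice weekly and allows restart after resolved toxicity, so disease-like events and rechallenge can both be expected.

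At stake is the input to the only numeric safety hold in the trial. Table 14 works with very small counts (1 of 5, 2 of 10, 3 of 16), so how a single participant is coded can matter. Because the five-level scale and the Yes/No question are not linked, two sites could also code the same event differently, and the plan does not say which answer is tallied.

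**Working it through.** **1. Category grid.** For an event related in time to dosing, section 11.3 yields:

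| | Does not recur on rechallenge | Recurs on rechallenge |
|---|---|---|
| Resembles disease | POSSIBLY | none |
| Distinct from disease | PROBABLY | DEFINITELY |

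Three of four cells have a category and one does not. This is a count of cells, not a frequency.

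**2. Where the unclassified event lies.** Elements missed, by category:

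- POSSIBLY: one (recurrence).
- DEFINITELY: one (distinctness).
- PROBABLY: two (distinctness, recurrence).
- UNRELATED and UNLIKELY: two each (timing, recurrence).

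The two nearest categories both count as related.

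**3. Section 6.4 against section 11.3.** Section 6.4 reaches only events at the POSSIBLY level or above, and it provides for repeat Grade 3–4 events after restart. Under section 11.3 the only related category that admits a recurring event is DEFINITELY, which excludes disease-like events. Read literally, the repeat-event provision cannot reach a disease-like toxicity that recurs. The two sections must be reconciled.

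**4. When the Table 14 count could change.** A first disease-like Grade 4 event, before any rechallenge, has not recurred and so fits POSSIBLY; that participant is already in the tally. A later recurrence adds nothing to a count of patients. A miss therefore needs one of two sequences:

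- a first event below Grade 4 that recurs at Grade 4; or
- a first Grade 4 event whose attribution is revised after rechallenge.

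**5. Table 14 reproduced.** With X binomial and a true Grade 4 rate of 0.10:

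- Look 1: P(X ≥ 2 of 5) = 1 − 0.9⁵ − 5(0.1)(0.9⁴) = 1 − 0.59049 − 0.32805 = 0.0815 (stated 0.081).
- Look 2: P(X ≥ 3 of 10) = 0.0702 (stated 0.070).
- Look 3: P(X ≥ 4 of 16) = 0.0684 (stated 0.068).

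Counting only trials not already held, the three looks contribute 0.0815 + 0.0318 + 0.0238 = 0.137. The stated cumulative figure of 0.219 is the plain sum 0.081 + 0.070 + 0.068; that is a separate matter and does not affect this point.

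**6. Sensitivity of the hold to uncounted participants.** Let f be the share of participants with a related Grade 4 event who go uncounted. The effective rate is p(1 − f); for example, 0.20 × 0.75 = 0.15. The documents give no value for f, so every non-zero f below is an assumption. Exact sequential probability of a hold:

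| True rate p | f = 0 | f = 10% | f = 25% | f = 50% |
|---|---|---|---|---|
| 10% | 13.7% | 11.0% | 7.4% | 3.1% |
| 20% | 49.9% | 42.2% | 30.7% | 13.7% |
| 30% | 80.7% | 73.2% | 59.0% | 30.7% |

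The rule is sensitive to missed participants. Step 4 shows that only two specific sequences can produce a miss, and nothing in the documents supports any particular f.

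**The case against.** A reader might infer that recurring, disease-like Grade 4 events are excluded from the safety count. The documents do not support that. Such an event fails UNRELATED and UNLIKELY as well, so the text leaves it unplaced; it does not code it as not related. The section 11.4 question would naturally be answered Yes after a positive rechallenge, and the threshold wording in sections 6.4 and 12 can be read in its ordinary sense to match that answer. This stands. It leaves a missing cross-reference and a category whose condition runs the wrong way, not a rule that removes events.

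A reader might also infer that seizures and peritumoral edema are documented cases of the gap. They are not. Section 6.6 reports that the edema cleared in every case while dosing continued, which is not recurrence on rechallenge. It describes seizures during high fever in patients with glioma and a known seizure disorder, with no rechallenge reported. They show only that drug effects can resemble the disease.

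Some backstops do not depend on attribution. Section 11.5 requires expedited reporting of all serious unexpected events and of serious events within 30 days of the last dose. Section 12 has the research monitor review every serious event and gives that monitor authority to stop the study. These limit the safety consequence, but they do not settle which participants Table 14 counts.

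It can also be said that section 6.4 already treats recurrence as a reason to act. It does, and that is why its wording and section 11.3 conflict.

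**Conclusion.** The definitional gap is exact: a timing-related, disease-like event that recurs on rechallenge meets none of the five categories, and positive rechallenge removes an event from POSSIBLY. Section 6.4 is inconsistent with this, and no section says whether the section 11.3 category or the section 11.4 answer feeds Table 14.

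The exposure is narrow and cannot be quantified from the documents. It is confined to the two sequences in step 4 of the working. This rests on two readings: that Table 14 counts patients, as its example does although its introduction speaks of events; and that an event not yet rechallenged satisfies the non-recurrence condition. The point is worth correcting because the change is cheap and protects the input to a hold that turns on one to three participants.

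**What to change.** - **Section 11.3:** remove the non-recurrence condition from POSSIBLY, and state that a timing-related event that recurs on rechallenge is at least POSSIBLY related whether or not it resembles the disease. Leave PROBABLY and DEFINITELY as they are. Deleting the condition from PROBABLY would make it overlap with DEFINITELY. Requiring at least PROBABLY for every recurrence is more than Table 14 needs, since an event such as a seizure in a patient with a known seizure disorder may recur by coincidence.
- **Section 11.4:** state that Possibly, Probably and Definitely equal Yes, and name that variable as the one counted for Table 14.
- **Section 6.4:** reconcile its relatedness wording with section 11.3 without changing any dose rule.

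The cost is a few sentences and matching form instructions, with no added participants or visits. The downside is that a few more events may be counted as related.

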11.4. Reporting Procedures for All Adverse Events

All observed or volunteered adverse events, regardless of suspected causal relationship to study drug, will be recorded as Adverse Events in the electronic case report forms and submitted via eDCS within 14 days of completion of each treatment cycle. Events involving adverse drug reactions, illnesses with onset during the study, or exacerbation of pre-existing illnesses should be recorded. Objective test findings (e.g. abnormal laboratory test results) should also be recorded if considered to be clinically significant by the treating investigator.

It will be left to the investigator's clinical judgment whether or not an adverse event is of sufficient severity to require that the participant should be removed from treatment. A participant may also voluntarily withdraw from treatment due to what he or she perceives as an intolerable adverse

event. If either of these occurs, the participant will be given appropriate care under medical supervision until symptoms cease or until the condition becomes stable.

The severity of toxicities will be graded in accordance with the Common Terminology Criteria for Adverse Event (CTCAE) version 5.0 ([CTCAE v5 Quick Reference](#)).

The relationship of adverse events to the study medications will be assessed by means of the question: "Is there a reasonable possibility that the event may have been caused by the study medication?", Please answer Yes or No.

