6.4. Dose Modifications for Toxicity

Dose modifications below apply to toxicities that are at least possibly related to study drug. Laboratory results requiring drug hold must be repeated weekly or sooner if clinically indicated until they meet the criteria for restarting drug.

Liver Toxicity

If AST/ALT > 5x ULN while on study, poly-ICLC will be held until the AST/ALT \leq 5x ULN; if resolved within 21 days, maintain the dose 20 mcg/kg/dose twice weekly.

If event resolves >22-28 days, hold study drug until values < 2.5x ULN then restart at the reduced dose of 10 mcg/kg/dose twice weekly.

If AST/ALT do not decrease to \leq 5x ULN within 28 days (despite holding the drug for 28 days and only if elevated AST/ALT is attributable to the drug), then the study drug will be stopped, and participant will be off treatment for toxicity.

It is recommended to evaluate other medications that participant is taking for potential liver toxicity (e.g. acetaminophen, trimethoprim/sulfamethoxazole, seizure medications). It is also recommended to evaluate potential viral liver infection if there is persistent elevation of AST/ALT.

Elevations of AST/ALT are expected, and repeat elevations do not require permanent drug discontinuation unless deemed medically necessary by the treating physician after discussion with the principal investigator.

Hematological Toxicities: Thrombocytopenia

Continue drug at 20 mcg/kg/dose unless platelet count is less than 75,000/mm³. Then refer to the table below for further instructions.

Platelet (Plt) < 75,000/mm ³	Interrupt study drug until Plt \geq 75,000/mm ³ . If the event resolves within 21 days, then study drug may be restarted at the same dose. If Plt count of <75,000/mm ³ attributable to the study drug, and the event resolves between 22-28 days, then study drug may be restarted at lower dose of 10 mcg/kg/dose. If Plt is <75,000/mm ³ after 28 days and at least "possibly" attributed to study drug, the participant will be taken off protocol therapy. Transient and repeated thrombocytopenia is expected and does not require permanent removal from study therapy unless deemed medically necessary by the treating physician after discussion with the principal investigator or study team.
---	---

Hematological Toxicities: Neutropenia

Continue drug same dose until absolute neutrophil count (ANC) is less than 750/mm³, then refer to the table below for further instructions.

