11. ADVERSE REPORTING REQUIREMENTS

11.1. Definitions

Adverse Events: An adverse event is any new, undesirable medical occurrence or change (worsening) of an existing condition in a participant that occurs from study enrollment until 30 days after drug discontinuation, whether or not considered to be product related. Therefore, adverse events are treatment emergent signs or symptoms. Elective hospitalizations for pretreatment conditions (e.g., elective cosmetic procedures) are not adverse events. Non-clinically significant abnormal laboratory values should not be reported as adverse events; however, any clinical consequences of the abnormality should be reported as adverse events. All adverse events must be noted on the electronic case report forms and submitted via eDCS within 2 weeks of completion of every treatment cycle.

For all adverse events, the investigator must pursue and obtain information adequate both to determine the outcome of the adverse event and to assess whether it meets the criteria for classification as a serious adverse event requiring immediate notification (within 24 hours) to the site PI and clinical coordinator, as well as the NFCTC Operations Center. Follow-up of the adverse event, even after the date of therapy discontinuation, is required if the adverse event or its sequelae persist. Follow-up is required until the event or its sequelae resolve or stabilize at a level acceptable to the investigator and sponsor.

Serious Adverse Events: A serious adverse event is defined by regulatory agencies as one that suggests a significant hazard or side effect, regardless of the investigator's or sponsor's opinion on the relationship to investigational product.

This includes, but may not be limited to, any event that (at any dose):
is FATAL;
is LIFE THREATENING (places the participant at immediate risk of death);
requires HOSPITALIZATION or prolongation of existing hospitalization;
is a persistent or significant DISABILITY/INCAPACITY; or
is a CONGENITAL ANOMALY/BIRTH DEFECT

Important medical events that may not be immediately life threatening or result in death or hospitalization but may jeopardize the participant or require intervention to prevent one of the outcomes listed above, or result in urgent investigation, may be considered serious. Examples include allergic bronchospasm, convulsions, and blood dyscrasias.

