11.5. Expedited Reporting Guidelines

The following adverse events require expedited reporting:

- All adverse events that are both serious and unexpected regardless of grade
- Adverse events that might influence the benefit-risk assessment of administration of poly-ICLC as outlined in the protocol
- All grade 5 adverse events
- A serious adverse event that occurs within 30 days of the last dose of the investigational agent
- Pregnancy

If a participant or a participant's partner becomes pregnant while receiving investigational therapy or within 30 days after the last dose of study drug, a report should be completed and expeditiously submitted as an SAE. Follow-up to obtain the outcome of the pregnancy should also occur. Abortion, whether accidental, therapeutic, or spontaneous, should always be classified as serious, and expeditiously reported as an SAE. Similarly, any congenital anomaly/birth defect in a child born to a female participant exposed to the poly-ICLC should be reported as an SAE.

- Expedited AE reporting timelines defined:

"24 hours; 3 business days" – The investigator must initially report the AE within 24 hours (or immediately if the event is fatal or life-threatening) of learning of the event to the Study Chair ([contact]) and NF Operations Center, followed by a complete written report within 3 business days of the initial 24-hour report.

Adverse events requiring expedited reporting will be reported and documented on **Form FDA 3500A MedWatch Form** <http://www.fda.gov/medwatch/getforms.htm>) and forwarded to:

NFCTC Operations Center

Clinical Research Manager: [name], BS

Program Director: [name], BS

Research Compliance Manager: [name], BS, CCRP

Direct Email: [contact]

The clinical research manager from the NFCTC Operations Center will forward all related adverse events that are both serious and unexpected to the FDA on **Form FDA 3500A MedWatch Form** <https://www.fda.gov/media/69876/download>:

MedWatch
Fax: [name]

The final MedWatch Form or CIOMS-1 form will be submitted by the Clinical Research Manager to Oncovir within one to two business days of submission to the FDA or applicable regulatory agency (including confirmation of date that the report was submitted) to allow Oncovir time to cross-report to Oncovir's IND. E-mail: [contact]; [contact].

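### Non-serious Grade 4 events count toward the Table 14 accrual hold but have no expedited route, so the hold can be missed with every reporting deadline met

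*Combined protocol and SAP*

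**What the plan says.** **The hold rule.** Section 12 says that Table 14 "defines the maximum allowed number of Grade 4 adverse events that are at least possibly attributable to the study drug". Neither seriousness nor expectedness is a condition. Accrual is held when more than 1 of 5, 2 of 10 or 3 of 16 patients have had such an event. The worked example ties the count to the next patient's start: "if 2 or more patients experience an event before the sixth patient begins therapy, the trial will be on hold". Section 14.3 adds that toxicity is monitored continuously.

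**Expedited reports.** Section 11.5 lists five triggers:
- "All adverse events that are both serious and unexpected regardless of grade";
- events that might alter the benefit-risk assessment;
- all Grade 5 events;
- any serious event within 30 days of the last dose;
- pregnancy.

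Each calls for a 24-hour report, a full written report within 3 business days and Form FDA 3500A. Section 11.1 separately requires 24-hour notice of any serious event to the Operations Center, expected or not.

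**Routine reports.** All other events "will be recorded as Adverse Events in the electronic case report forms and submitted via eDCS within 14 days of completion of each treatment cycle" (Section 11.4; Section 11.1 gives the same two weeks). Section 13.4 sets a general deadline of two weeks after each required evaluation.

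**Laboratory values.** Section 11.1 states: "Non-clinically significant abnormal laboratory values should not be reported as adverse events". Section 11.4 leaves that judgment to the treating investigator. Section 6.4 manages AST/ALT, platelets and neutrophils by name and says "Elevations of AST/ALT are expected, and repeat elevations do not require permanent drug discontinuation". It describes recurrent thrombocytopenia and neutropenia in similar terms.

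**The concern.** The rule needs a complete and current count of related Grade 4 events each time a patient is about to start. The reporting sections guarantee such a count only for events that are also serious. Nothing in the protocol equates Grade 4 with serious. In Section 11.1 life-threatening means an immediate risk of death, and important medical events, with blood dyscrasias as an example, only may be classed as serious. The first trigger in Section 11.5 also treats grade and seriousness as separate properties. A Grade 4 neutrophil, platelet or transaminase value without hospitalization can therefore be non-serious and still count toward the hold.

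At stake is exposure of a further child to the drug after the threshold has been crossed but before anyone keeping the count can know it. There is also a definitional gap: a Grade 4 laboratory value may trigger a drug interruption under Section 6.4 and yet, on the investigator's judgment, not be an adverse event at all.

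**Working it through.** **1. The plan's own figures.** Section 12 says "Safety rules were generated using a binomial distribution". With a true rate of 0.10 and m events permitted among n patients, P(X ≥ m+1) is:

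| n | m | Table 14 | Recomputed |
|---|---|---|---|
| 5 | 1 | 0.081 | 1 − 0.9^5 − 5(0.1)(0.9^4) = 0.0815 |
| 10 | 2 | 0.070 | 0.0702 |
| 16 | 3 | 0.068 | 0.0684 |

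The per-look column reproduces. It assumes that each patient's outcome is known when the look is taken.

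**2. Route by type of related Grade 4 event.**

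| Event | Route | Permitted interval |
|---|---|---|
| Serious, expected or not | 11.1; 11.5 | 24 hours |
| Non-serious adverse event | 11.1 and 11.4 | 14 days after cycle end |
| Same, if found at a required evaluation and 13.4 governs | 13.4 | 14 days after that evaluation |
| Laboratory value judged not clinically significant | not an adverse event under 11.1 | none |

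**3. Interval on the routine route.** Inputs: cycle of 28 days, up to 33 with the window (Section 4.2), and 14 days to submit. Interval = days left in the cycle + 14.

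- Just after day 1: 28 + 14 = 42; 33 + 14 = 47 (41 and 46 in days elapsed since day 1).
- Cycle 1 day 8: (28 − 8) + 14 = 34; (33 − 8) + 14 = 39.
- Cycle 1 day 15: (28 − 15) + 14 = 27; (33 − 15) + 14 = 32.
- Last day of a cycle: 14.

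**4. Patients expected to start in that interval.** Inputs: 20 patients in 36 months (Section 14.2). Even accrual is assumed. Rate = 20 / 36 / 30.4375 = 0.01825 per day.

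| Interval (days) | Expected starts | Chance of at least one (Poisson assumed) |
|---|---|---|
| 14 | 0.26 | 23% |
| 27 to 32 | 0.49 to 0.58 | – |
| 34 to 39 | 0.62 to 0.71 | – |
| 42 to 47 | 0.77 to 0.86 | 54% to 58% |
| 1 (24-hour notice) | 0.02 | – |

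**5. Why the laboratory definition matters.** The documents give neither a Grade 4 rate nor the share that would go unrecorded, so this is illustration, not estimate. The exact probability of a hold by the third look, if all, three quarters or half of affected patients are counted, is:

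| True rate | All | 75% | 50% |
|---|---|---|---|
| 0.10 | 0.14 | 0.07 | 0.03 |
| 0.20 | 0.50 | 0.31 | 0.14 |
| 0.30 | 0.81 | 0.59 | 0.31 |

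**The case against.** **Section 13.4 may already close most of the gap.** Section 5.2 requires toxicity monitoring at every visit, and Appendix 3 schedules a toxicity evaluation on cycle 1 days 1, 8 and 15 and before each later cycle. If these are required evaluations in the sense of Section 13.4, an event found there is due in 14 days. This reading is plausible. But it conflicts with the deadline written specifically for adverse events, the protocol does not say which prevails, and 14 days still leaves 0.26 expected starts.

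**The longest interval does not fit scheduled laboratory tests.** After cycle 1 day 1 the next scheduled blood count is day 8, and AST/ALT is next scheduled at cycle 2 day 1. Later tests fall around day 1, and values failing Section 4.2.1 prevent the next cycle from starting. Such an event ordinarily belongs to the cycle just ended and is due in about 14 days. This stands: 42 to 47 days applies only to events outside the laboratory schedule.

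**There is other oversight.** The study chair approves each enrollment, there are monthly calls, a research monitor and a DSMB, and Section 13.7 refers to a separate multi-center monitoring plan that was not available here. That plan may assign the count. In the protocol itself, monthly reports address completeness, the calls address quality assurance, and nobody is given the Table 14 count.

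**Sites could expedite anyway,** through the benefit-risk trigger or by classing the event as medically important. Both are discretionary, and describing these toxicities as expected does not encourage their use.

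**Adding all Grade 4 events to the Section 11.5 list is burdensome,** because every entry needs Form FDA 3500A and a full written report. This stands, and the fix avoids it.

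**Conclusion.** The point holds for non-serious Grade 4 events at least possibly related to the drug, expected or not. They count toward the hold, have no expedited trigger, and may lawfully be unreported when the next patient starts. The size is 0.26 to 0.86 expected further starts per event, assuming even accrual; clustered accrual would make it larger.

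Three stronger readings are tempting and are not supported:

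- A reader might infer that expected Grade 4 events in general escape expediting. They do not if serious: Section 11.1 and the fourth trigger in Section 11.5 carry no condition of unexpectedness.
- A reader might infer that reports will arrive up to 47 days late and that the rule cannot work. The figure is a permitted worst case, not lateness or a typical delay, and it corresponds to fewer than one expected start. Nor is it a firm ceiling, since the text does not say how a drug interruption affects cycle completion.
- A reader might infer that laboratory toxicities will never reach the count and that the toxicity endpoint is certainly too low. This would require an investigator to judge a Grade 4 value not clinically significant. By definition that value is then not an adverse event, so its place in Table 14 is undefined rather than shown to be missed, and no undercount can be estimated from the documents.

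**What to change.** 1. Require sites to notify the Operations Center within 24 hours of learning of any Grade 4 adverse event at least possibly related to poly-ICLC, whether or not serious or expected. A short eDCS or email notice is enough; Form FDA 3500A applies only if the event otherwise qualifies under Section 11.5. The Operations Center keeps the Table 14 count and checks it before confirming each treatment number under Section 3.3.3.
2. Reconcile the Section 13.4 deadline with Sections 11.1 and 11.4, and state which governs adverse events.
3. State in Sections 11.1 and 11.4 that any Grade 4 laboratory value, or any value that triggers an interruption, reduction or removal under Section 6.4, is recorded as an adverse event regardless of judged clinical significance.

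The cost is a short amendment and a few extra brief notices from at most 20 patients. No tests or visits are added and the hold thresholds do not change. The recorded Grade 4 count may rise slightly, which would make a hold somewhat more likely.
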